## Mapping/ Transect Walk Observation Checklist

Places	
1 Health facility	
1.1 Formal	6.3 Beauty salon
1.2 Informal	6.4 Shop selling pharmaceuticals
2 Other places linked to HIV testing and treatment	6.5 Stall selling pharmaceuticals
2.1 Pharmacies	6.6 Other
2.2 Drug stores	7 Stations / bus stops
2.3 Trading places/ stores that sell drugs, syringes etc	7.1 Bus
3 Place of worship (what denomination?)	7.2 Mini Bus
4 Recreational spaces	7.3 Railway
4.1 Library/ schools	7.4 Taxi rank
4.2 Sports venue/ open ground	7 NGO
4.3 Disco	9 School
4.4 Community hall	10 Residential housing (what type?)
4.5 Video club	11 Boundary landmark
4.6 Other	12 Police Post
5 Alcohol outlet	13 Other (AS SUGGESTED BY LOCAL EXPERTS)
5.1 Bar	
5.2 Night club	
5.3 Shebeen (informal)	
5.4 Lodge	
5.5 Other	
6 Commercial Premises	
6.1 Market area	
6.2 Shop	

Notes:

1. TIME
2. TYPE OF PLACE (see list of places above)
3. STRUCTURE OF BUILDING – large / small (estimate in metres); new / old; cramped / spacious; well ventilated / not well ventilated (explain why); temporary / permanent; building materials – brick, concrete, grass, mud; etc.
4. PEOPLE - busy / quiet; estimate number of men / women / children; estimate average age of children / youth / adults / elderly present
5. ACTIVITY - what is happening? (E.g. playing football, watching a video, waiting, drinking etc.). Also if there is an event (e.g. football match, fight, outreach education etc), note this.
6. RELEVANCE TO HIV/ HIVST – note or sketch briefly of particular relevance and write up in more detail later. Note areas where HIV testing is done, where people go for treatment, where people access drugs etc.
7. Record all the words for HIV or ARVs or HIV testing (vernacular, English, slang, street language) that you have heard during this observation

## **Transect Walk Guide**

### **Objectives:**

1. Observations of the range of HIV services.
2. Observe activities and movement of different social, age and gender groups.
3. Observe interactions between people and between people and activities
4. Gain a rapid understanding of places of significance to the management of HIV, including any areas where HIV mobile testing is held.
5. Identify places that pharmaceutical drugs and items are sold.

**RA Roles:** Both RAs to chat to local people during the transect walk.

**Materials:** Transect Walk Guide, map of community with transect walk plotted on (drawn by neighbourhood health committee), GPS, GPS Data Capture Sheet (see tools), Transect Walk Observation Guide, few sheets of A4 paper, notebook, pens.

**Time of Activity:** Afternoon and Morning.

**Length of Activity:** One afternoon and one morning.

**Venue:** No venue; rather going in concentric circles from the 'centre' of community and also following the lead from social and resource maps earlier drawn by participants of FGDs

### **Flow:**

#### **At the start:**

- Set off from health centre and move from there from place to place using the administrative divisions of the community such as zones and or sections as a guide.

#### **During the walk:**

1. Observe the places passed, noting conditions in different sub-areas and housing clusters, activities and movements of people and livelihood options.
2. Ask others who they pass probing questions about the different housing clusters and important places in the area with regard to managing HIV in this place, including testing

options and specifically if they have heard about HIVST. Make rough notes or sketches in the notebook.

3. Look out for the types of places suggested by the Transect Walk List of Places i.e. health facilities, commercial premises, places of worship, recreational spaces, boundary landmarks, graveyard, etc (see TRANSECT WALK OBSERVATION CHECKLIST). Stop at each such place.
4. Look out for places where mobile HIV testing is held and where HIV testing is more frequently available. And where HIVST could be conducted.
5. Note any stalls/ tuntembas, shops and market areas where pharmaceutical products are sold.
6. For each place:
  - a. The waypoint number and coordinates are recorded on the GPS DATA CAPTURE SHEET.
  - b. The type of place (selected from the TRANSECT WALK OBSERVATION CHECKLIST) and the name of this particular place (if applicable) are indicated.
  - c. A description is given of: type of gathering place; size of building; what people are doing; the approximate number of people; the age mix of people there.
  - d. Assess whether the place is a possible observation point to return to on the following days.
  - e. If people ask, explain that the team are doing this for the purposes of understanding the community before a new HIV project begins. Engage in brief informal conversation, making field notes afterwards.

**Data Collected and Stored:**

1. Make a rough sketch of the transect walk on blank A4 paper, indicating all the places plotted and observed during the walk.
2. Complete the Transect Walk Activity Report Form on the same days as carrying out the walks, describing the process and the findings (from notes made in the note book) as they relate to activities and mobility of people and perceptions of HIV transmission, testing and prevention.
3. Record all the words for HIV/ ARVs/ HIVST (vernacular, English, slang, street language) that you have heard during this observation.
4. Record any discussions specific to HIV testing and HIV self-testing.

### **Transect Spiral Walk ACTIVITY REPORT FORM**

1. Date and place conducted:
2. Time taken and rough estimate of distance:
3. Observation of Place not captured in the Data Capture Sheets including: what people are there (ages, gender, local/not local); relevant IEC material/other visuals; activities during the day; movement of people; interactions between people; activities; gossip; entry/exit points: (use an extra pieces of paper to sketch any maps if helpful and attach)
4. Any observations of places/activities of significance to HIV transmission:
5. Any observations of places/activities of significance to HIV testing, drug marketing and distribution
6. Any information specifically on range, type of health services related to HIV:
7. Any information specifically on HIV/ HIVST testing:
8. Any information on HIV counselling:
9. Any information social harms related to HIV/ HIVST testing:
10. Record any words/phrases you have heard people use to talk about HIV, HIV testing, ART, counselling, and social harms (English, slang, vernacular, street etc...):
11. Any additional observations of relevance:

## **Stakeholder Analysis Discussion Guide/ IDI**

Purpose: To identify HIVST CS stakeholders and map their activities vis-à-vis those of the HIVST CS.

Objectives:

1. To describe popular understandings of HIV/ HIVST among stakeholders in HIVST CS communities
2. To describe the strategies and processes supporting implementation of HIV/ HIVST-related services in the communities
3. To explore perceptions HIV/ HIVST treatment and care from stakeholders' perspectives
4. To describe the influence of HIV/ HIVST-stigma on the uptake and adherence to HIV/ HIVST treatment from a stakeholder 'perspective'
5. To explore the interaction between the stakeholders and the potential interactions between stakeholders and the HIV/ HIVST study.

Form of data recording: (1) Audio-recording of all talk from "Preamble" to "Closing". (2) Notes of key points per topic area handwritten by the facilitator into a printed copy of this document. (3) Photographs of each of the activities. (4) Handwritten notes by participants during the discussion.

Expected time needed: 45 minutes

Date activity conducted: \_\_\_\_\_

Place conducted: \_\_\_\_\_

Time period: \_\_\_\_\_

Preamble (to be read by facilitator): Today is the ([insert date] and it is [insert time]. This is a discussion with an implementing staff at (XXXX) Clinic. Thank you for your time. All information collected here will be reported anonymously. May I remind you that we are audio recording this discussion and ask that you speak loudly and clearly. As the facilitator, I will also be taking some notes. Do you have any questions before we begin?

### **INTRODUCTION [2 minutes]**

We have selected all of you to represent your community because of the role you play related to provision of HIV/ HIVST services. We ask you to be free to share as much as can during the discussion/ meeting.

### **Topic Area 1 – Description of Stakeholder**

(Facilitator to read bolded text below and elaborate with prompts at their discretion)

## Activity: Stakeholder Profile

Open the meeting with a short ‘presentation’ on what HIV/ HIVST is and allow for time to respond to questions the stakeholders may have.

Variable	– Task	Objectives
Name	
 
– Distribute plain coloured cards (half of A4 size) to each stakeholder participant.
 
– Ask them to write the name of the organization they are representing on top of the paper.
 
– Below it ask them to write the year they started working in the HIVST CS community.
 
	Identify stakeholders
Period	
 
– Collect the papers from the participants and stick them on a wall according to the year they started working in the community.
 
	Period service delivery
Involvement	
 
– Give them A4 size paper to write/list the activities or services they provider in bullet form.
 
– Collect the papers and stick them below the earlier paper with name of stakeholder and the year –leave small space in-between.
 
	Whether HIV/ HIVST service delivery is primary objective
Interest	
 
– Ask them to list HIV/ HIVST activities or services they provide in the community, or what they do to assist their clients/patients’ concern on HIV/ HIVST (List HIV/ HIVST activities/services).
 
– After they list down, collect the papers and place them under the organisations’ names on the wall.
 
	Whether HIV/ HIVST service delivery is secondary/tertiary objective
Influence	
 
– Ask them if they work together with other organizations in any way on HIV/ HIVST related activities (should write this on separate A4 papers).
 
– Ask them to write about how they think HIV/ HIVST will influence their work; positive/negative?
 
– Ask them if they at all worked or collaborated with the CHiPs on HIV/ HIVST activities.
 
– If any of the stakeholders did, ask them to list the role they played with the CHiPs (should write this on separate paper).
 
– List other stakeholders not present.
 
	Influence of stakeholder on HIV/ HIVST service delivery in the community.
Alignment	
 
– Ask them to explain the groups, age, gender, and areas they work with/ from in the community.
 
	Groups targeted and not targeted

After the stakeholder profile activity has been completed you may ask questions from the topic areas below to complement information gathered above. If it is not possible to gather all the required information for all the stakeholders, schedule specific meetings with the affected stakeholders as well as those that were not present.

#### Topic Area 2 – HIV/ HIVST specific activities

1. **Do you do any HIV/ HIVST related activities?** What do you do? Why? When do you do them? Do you work with the clinic? How long have you worked with the clinic?
2. **How has working in this community been?** Do you specifically work with HIV/ HIVST patients? How do you identify them? Are there any specific places where these people are found? Do you find it challenging working with them? Why?
3. **Do you give any kind of support to HIV/ HIVST patients?** What do you give? When do you give?
4. **Which HIV/ HIVST programs have you done in the past?** What were you trying to achieve? What worked well/ did not work well? What do you think would have been done better? Which HIV/ HIVST programme are you implementing now? Do you collaborate with other organisations in your implementation? Which organisations are those? Why?
5. **Are there any other organisations which conduct HIV/ HIVST related activities you know of in this community?** Do they come from outside the community? Where do they work from? Who do they work with? What kind of activities do they do? How long have they worked in this community?

#### Topic area 3 – Knowledge, Training and Experience

1. **How have HIVST CS activities (i.e. anything to do with HIVST CS) affected activities (i.e. anything to do with HIV/ HIVST treatment and care) in the community?** Do you think that HIVST CS HIV/ HIVST screening increased the number of people diagnosed and treated for HIV/ HIVST at the clinic? Were any other people/organisations involved in the implementation of HIV/ HIVST treatment provision? Please describe these people/organisations and what they did and how they contributed to HIV/ HIVST services in the clinic and community.
2. **What has your experiences of delivering HIV/ HIVST services in this community been like?** Are there any particular challenges to providing HIV/ HIVST services in this community?
3. **Please tell me about any efforts to promote facility-based HIV/ HIVST screening.** What are some of the initiatives that were implemented to promote HIV/ HIVST treatment uptake? Which facility-based health workers were involved and how? Over what period were these efforts implemented? How did you prioritise who to screen for HIV/ HIVST? (Prompt: Specific

services access? Ages? Gender?) What do people say when they don't want to screen for HIV/ HIVST?

4. **Were there any efforts that focused on particular groups of people?** Did you notice any differences in the age groups, or other characteristics, of those coming to the clinic? Did you get the impression that clients were more/less willing to screen for HIV/ HIVST at certain times of the day, month or year?

#### Topic area 4 – HIV/ HIVST and Stigma

1. **Has the way that people talk about HIV/ HIVST in the community/ organization changed over the years?** What did they used to say about HIV/ HIVST? What do they say now? Are people living with HIV/ HIVST more or less stigmatised now than they were in the past? What do you think has contributed to the change?
2. **From what you know/ have seen, does the fear of being stigmatised stop people living with HIV/ HIVST from seeking treatment/ care?** Can this also delay diagnosis of HIV/ HIVST? If HIV/ HIVST was not stigmatized, would people get treatment sooner? Why? Do you know of people living with HIV/ HIVST who are afraid to ask their friends and family for help? Can you give an example of this?

Name of Stakeholder	What the stakeholder does	Influence on/ by HIVST CS	Locations/ contact details

## Social harms and Incidents Grading

### Questions from the CE 3ie

	GRADE 1 (MILD)	GRADE 2 (Moderate)	GRADE 3 (Severe)	GRADE 4 (Potentially life-threatening) (Within 30 days)
Definitions	Mild symptoms causing no or minimal interference with usual social & functional activities with intervention not indicated	Moderate symptoms causing greater than minimal interference with usual social & functional activities with intervention indicated	Severe symptoms causing inability to perform usual social & functional activities with intervention or hospitalization indicated	Potentially life-threatening symptoms causing inability to perform basic self-care functions with intervention indicated to prevent permanent impairment, persistent disability, or death

Description	
Verbal, emotional or psychological Intimate-Partner Violence (IPV)
 
Denying access to household resources
 
Being ignored
 
Being controlled (e.g. not allowed to leave house)
 
Being shouted at
	
Coercion to self-test.
 
Coercion to disclose a self-test result
 
IPV that includes e.g. pushing, or slapping with an open hand that does not result in pain or visible marks >24hrs
 
Threatened Severe physical violence
 
Psychologically coercive sex.
 
Being discriminated
	
IPV that leads to pain, bruising or marks >24hrs.
 
Verbal threats of potentially lethal violence (e.g. statement of intent to kill, mock strangulation, threatened with a knife or gun
 
Physically coercive sex
 
Marriage break-up
	
IPV leading to hospitalization or death
 
Suicide or attempted suicide
 
Attack using potentially lethal force (e.g. knife, gun, hammer, kicks to head, asphyxiation)
 
Tingling of the gum as a result of oral swabbing

-------------	---	--	--	--

Steps to follow	
 
• Referred to community-based institutions for assistance. e.g. CBOs, Police.
 
	
 
• Referred to community-based institutions for assistance.
 
• Reported to relevant authorities. E.g. Community Liaison Officer.
 
• Refer to community-based GBV support organizations
 
	
 
• Report to marriage councillors
 
• Report to relevant authorities. E.g. Community Liaison Officer.
 
• Refer to community-based GBV support organizations
 
	
 
• Report to police/chief (Homicide)
 
• Report to police (Suicide)
 
• Report to relevant authorities e.g. Community Liaison Officer
 
• Report to CLO (Tingling of the gum)
 
• Refer to community-based GBV support organizations
 
• Ensure safe alternative abode before discharge
 

-----------------	---	---	---	---

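### The social-harms table puts gum tingling in Grade 4 and leaves the Grade 3 marriage-councillor step tied to no event

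*Protocol*

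**What the plan says.** Section 10.2 states that the protocol already contains a grading system for judging incidents. The only social-harms grading shown is the four-column table in Appendix 4, Social harms and Incidents Grading, sub-headed as coming from the 3ie work. It has a definition row, a description row and a row of steps to follow.

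- **Grade 3 (severe), description.** Four events: "IPV that leads to pain, bruising or marks" lasting more than 24 hours, verbal threats of potentially lethal violence, "Physically coercive sex" and "Marriage break-up".
- **Grade 3, steps.** Three bullets: "Report to marriage councillors", a report to relevant authorities such as the Community Liaison Officer (CLO), and referral to community organisations that support survivors of gender-based violence (GBV).
- **Grade 4, definition.** "Potentially life-threatening symptoms causing inability to perform basic self-care functions", with intervention needed to prevent permanent impairment, persistent disability or death.
- **Grade 4, description.** Four entries: partner violence leading to hospitalisation or death, suicide or attempted suicide, attack with potentially lethal force, and "Tingling of the gum as a result of oral swabbing".
- **Grade 4, steps.** Six bullets. Three carry an event in brackets, including "Report to police/chief (Homicide" and "Report to CLO (Tingling of the gum" (closing brackets omitted here). The other three are a report to relevant authorities, referral to GBV organisations, and securing safe accommodation before discharge.

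Section 10.2 separately sends known individuals who report serious harms, GBV among them, to the counsellor at the health facility, who can refer onward. Its list of onward bodies is open-ended.

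**The concern.** A grading table has to be usable by the person who looks an event up in it. Two cells here are not.

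The first is a plain misgrading. Tingling from an oral swab sits at the same level as attempted suicide and lethal attack, and above physically coercive sex. Objective 4 of section 2.2 is to evaluate how often social harms occur and what they are. If harms are summarised by this scale, each report of tingling is counted at its highest grade. Section 10.2 also points to the grading when it discusses whether an incident is serious enough to follow up.

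The second is an ambiguous instruction. The Grade 3 column is mostly violence, and one of its actions is a report to marriage councillors with no statement of which event it serves. Section 10.2 itself acknowledges that giving a woman a kit for her partner may carry a serious risk of GBV. The one-month follow-up questionnaire in Appendix 3 asks index participants about being hit or choked and about forced sex. Staff will therefore be asking about events that fall in this column.

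**Working it through.** No calculation applies and the plan gives no figure to reproduce. The check sets the rows of the table against each other and against sections 10.2 and 8.4.

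1. **Tingling against the Grade 4 definition.** The definition requires life-threatening symptoms and loss of basic self-care. Three of the four Grade 4 entries are compatible with that; tingling of the gum is not. The Grade 1 definition (mild symptoms, little or no interference with usual activities, no intervention needed) describes it well. Entries that do not fit: 1 of 4.

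2. **Is it an extraction artefact?** Tingling appears in the Grade 4 column of the description row and again in the Grade 4 column of the steps row, where it has its own CLO report. A shifted cell would have to have moved the same way in two rows, so the placement appears to be the authors' own.

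3. **Ordering.** Physically coercive sex is Grade 3 and tingling is Grade 4, so the scale ranks tingling as the worse event.

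4. **The marriage-councillor step against the Grade 3 events.**

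| Grade 3 event | Does a report to marriage councillors suit it? |
|---|---|
| Partner violence with pain or marks beyond 24 hours | No |
| Verbal threat of potentially lethal violence | No |
| Physically coercive sex | No |
| Marriage break-up | Yes |

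The step suits 1 of 4 events. An event is named in 0 of 3 Grade 3 steps and in 3 of 6 Grade 4 steps, so the table already has a convention for tying a step to an event and does not use it here.

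5. **How far the missing qualifier goes.** Two of the three unqualified Grade 4 steps, safe accommodation and GBV referral, cannot sensibly apply to tingling, which is in their column. A bullet without a bracket therefore does not always mean every event in the column. The Grade 3 step is open to a wrong reading; the text does not compel that reading.

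6. **Against section 10.2.** The steps number 1 + 3 + 3 + 6 = 13 across Grades 1 to 4. Section 10.2 concerns serious harms, so Grades 3 and 4 are the natural comparison (3 + 6 = 9 steps). The health-facility counsellor is in none of the 9, nor in the other 4. This is a gap in alignment. The two texts can both be followed.

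7. **Against section 8.4.** That section requires Grade 4 events suspected to be procedure reactions to be reported within two working days. It introduces the list by citing an external adverse-event reporting manual (reference 25). Its Grade 4 need not be the Grade 4 of this table.

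**The case against.** The best case for the table is that its readers are trained and supervised. Sections 3, 8.4 and 10.2 provide training on harms and referral, confirmation and categorisation by a supervisor, assessment of seriousness and relatedness by the principal investigator, and an existing procedure for reporting social harms. Marriage break-up is in the Grade 3 column and is the obvious partner of the marriage-councillor step. Tingling has its own CLO step, so nobody is sent to the police for it, and grading it too high errs towards over-reporting. All of this stands. It limits the consequence, but it does not make tingling life-threatening or say which event the marriage-councillor step serves.

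A reader might infer four stronger things that the documents do not support:

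- *That all Grade 3 cases, including forced sex, must go to marriage councillors.* Other unqualified steps plainly do not cover their whole column, so this does not follow.
- *That marriage councillors come first.* The bullets are unnumbered; list order is not a stated priority.
- *That the table contradicts section 10.2 or that a safeguard is missing.* The counsellor referral in section 10.2 still applies, its list of onward bodies is open, and the Grade 3 cell keeps the authority and GBV-organisation steps.
- *That tingling triggers the two-working-day report.* Section 8.4 rests on a cited external manual, so the documents do not establish that link.

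**Conclusion.** The point holds in two parts of unequal strength. The misgrading of tingling is a clear error: one of four Grade 4 entries conflicts with the definition in its own column. The marriage-councillor step is an ambiguity: one of three Grade 3 steps names no event and suits one of four. It matters because the other three events are violence, lethal threat or sexual coercion. The counsellor's absence from the table is a matter of alignment only.

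This rests on two assumptions: that the table is the grading section 10.2 refers to, being the only one shown, and that staff consult it when they grade and act on a harm. Any effect on objective 4 further assumes that harms are summarised by grade. No delay, number of cases or effect on sample size or the primary analysis is claimed. It should be corrected because it concerns participant safety and the change is nearly free.

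**What to change.** In the description row, move tingling of the gum from Grade 4 to Grade 1. In the steps row:

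- move its CLO report to Grade 1 with it;
- extend "Report to marriage councillors" with the bracketed event *(Marriage break-up)*, in the style of the Grade 4 cell;
- add referral to the counsellor at the health facility, citing section 10.2, for Grade 3 events and for Grade 4 survivors, with no order imposed;
- keep all existing authority, GBV-organisation, police and safe-accommodation steps.

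The cost is edits to two rows of one appendix table and a short staff briefing. Data collection, sample size and analysis do not change.
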